8.1 Site monitoring

Before study initiation, at a site initiation visit or at an investigator's meeting, a Novartis representative will review the protocol and CRFs with the investigators and their staff.

The investigator must give the monitor access to all relevant source documents to confirm their consistency with the CRF entries. Novartis monitoring standards require full verification for the presence of informed consent, adherence to the inclusion/exclusion criteria, documentation of SAEs, and of data that will be used for all primary variables. Additional checks of the consistency of the source data with the CRFs are performed according to the study-specific monitoring plan. No information in source documents about the identity of the patients will be disclosed.

8.2 Data collection

Designated investigator staff must enter the information required by the protocol onto the Novartis CRFs that are printed on 3 -part, non-carbon-required paper. Field monitors will review the CRFs for completeness and accuracy and instruct site personnel to make any required corrections or additions. The CRFs pages will be collected by field monitors after monitoring validation, with one copy being retained at the investigational site. Once the CRFs pages collected, the original copy will be placed in the study Trial Master file, and the non- carbon-required copy will be forwarded to the CRO in charge of Data Management for processing.

8.3 Database management and quality control

Data from the CRFs will be entered into the study database by CRO staff, using double data entry and following their own internal standard operating procedures (that have been reviewed and approved by Novartis).

Subsequently, the entered data will be systematically checked by Data Management staff, using error messages printed from validation programs and database listings. Other errors or omissions will be entered on Data Query Forms, which will be returned to the investigational site for resolution. The signed original and resolved Data Query Forms will be kept with the CRFs at the investigator site, and a copy will be sent to the CRO so the resolutions can be entered into the

database. Quality control audits of all key data in the database will be made prior to locking the database.

Adverse events will be coded using the Medical dictionary for regulatory activities (MedDRA) terminology.

After these actions have been completed and the database has been declared to be complete and accurate, it will be locked. Any changes to the database after that time can only be made after written agreement by Novartis.

8.4 Data Monitoring Committee

Not required.

8.5 Adjudication Committee

Not required.

9 Data analysis

9.1 Analysis sets

Safety Set: Consists of all patients who received at least one dose of study drug and had at least one post-treatment safety assessment in the study. The statement that a patient had no adverse event (AE) also constitutes a safety assessment.

9.2 Patient demographics and other baseline characteristics

Demographics, background data and key baseline characteristics are those collected in the CACZ885G2301E1 study. Sex and date of birth will be re-collected in the CRF.

9.3 Treatments

The exposure to study drug (number of injections) and duration of exposure (days) will be summarized and listed by dose.

9.4 Analysis of variables

9.4.1 Variables

a. Efficacy variables

There is no efficacy assessment in this study

b. Safety variables

Adverse events will be coded using the MedDRA dictionary that provides the primary system organ class and preferred term information. Adverse events will be presented in two parts:

- Adverse events (including infections)
- Infectious adverse events

Adverse events will be summarized for each disease by presenting the number and percentage of patients having any adverse event, having any adverse event in each primary system organ class and having each individual adverse event based on the preferred term. All other information collected (e.g. severity, relationship to study drug, or microorganism for infectious adverse events) will be tabulated and listed as appropriate.

Deaths, serious adverse events, and adverse events leading to discontinuation of study drug will be summarized by primary system organ class and preferred term and listed.

9.4.2 Statistical model, hypothesis, and method of analysis

This is an open-label single-arm safety trial for patients and the data will be presented in a descriptive manner.

9.4.3 Handling of missing values/censoring/discontinuations

Missing values will not be handled but premature discontinuation will be fully described.

9.5 Interim analyses

Not required

9.6 Sample size calculation

No sample size calculation was performed for this extension study which will include all eligible subjects who complete CACZ885G2301E1 or CACZ885N2301 study and meet the eligibility criteria.

10 Ethical considerations

10.1 Regulatory and ethical compliance

This clinical study was designed and shall be implemented and reported in accordance with the ICH Harmonized Tripartite Guidelines for Good Clinical Practice, with applicable local regulations (including European Directive 2001/20/EC, US Code of Federal Regulations Title 21, and Japanese Ministry of Health, Labor, and Welfare), and with the ethical principles laid down in the Declaration of Helsinki.

10.2 Informed consent procedures

Eligible patients may only be included in the study after providing written (witnessed, where required by law or regulation), IRB/IEC-approved informed consent, or, if incapable of doing so, after such consent has been provided by a legally acceptable representative of the patient. In cases where the patient's representative gives consent, the patient should be informed about the study to the extent possible given his/her understanding. If the patient is capable of doing so, he/she should indicate assent by personally signing and dating the written informed consent document or a separate assent form. Informed consent must be obtained before conducting any study-specific procedures (i.e. all of the procedures described in the protocol). The process of obtaining informed consent should be documented in the patient source documents.

Novartis will provide to investigators in a separate document a proposed informed consent form that complies with the ICH GCP guideline and regulatory requirements and is considered appropriate for this study. Any changes to the proposed consent form suggested by the investigator must be agreed to by Novartis before submission to the IRB/IEC, and a copy of the approved version must be provided to the Novartis monitor after IRB/IEC approval.

Women of child bearing potential should be informed that taking the study treatment may involve unknown risks to the fetus if pregnancy were to occur during the study and agree that in order to participate in the study they must adhere to the contraception requirement for the duration of the study. If there is any question that the patient will not reliably comply, they should not be entered in the study.

10.3 Responsibilities of the investigator and IRB/IEC

The protocol and the proposed informed consent form must be reviewed and approved by a properly constituted Institutional Review Board/Independent Ethics Committee/Research Ethics Board (IRB/IEC) before study start. A signed and dated statement that the protocol and informed consent have been approved by the IRB/IEC must be given to Novartis before study initiation. Prior to study start, the investigator is required to sign a protocol signature page confirming his/her agreement to conduct the study in accordance with these documents and all of the instructions and procedures found in this protocol and to give access to all relevant data and records to Novartis monitors, auditors, Novartis Clinical Quality Assurance representatives, designated agents of Novartis, IRBs/IECs, and regulatory authorities as required. If an inspection of the clinical site is requested by a regulatory authority, the investigator must inform Novartis immediately that this request has been made.

10.4 Publication of study protocol and results

Novartis assures that the key design elements of this protocol will be posted in a publicly accessible database such as clinicaltrials.gov. In addition, upon study completion and finalization of the study report the results of this trial will be either submitted for publication and/or posted in a publicly accessible database of clinical trial results.

11 Protocol adherence

Investigators ascertain they will apply due diligence to avoid protocol deviations. Under no circumstances should the investigator contact Novartis or its agents, if any, monitoring the trial to request approval of a protocol deviation, as requests to approve deviations will not be granted.

This protocol defines the study objectives, the study procedures and the data to be collected on study participants. Under no circumstances should an investigator collect additional data or conduct any additional procedures for any research related purpose involving any investigational drugs.

If the investigator feels a protocol deviation would improve the conduct of the study this must be considered a protocol amendment, and unless such an amendment is agreed upon by Novartis and approved by the IRB/IEC it cannot be implemented. All significant protocol deviations will be recorded and reported in the CSR.

13 Appendix 1: Summary of product characteristics

2.12	Biomarkers.....	14
2.13	Other Exploratory analyses.....	14
2.14	Interim analysis.....	14
3	Sample size calculation	14
4	Change to protocol specified analyses	14
5	Appendix	14
5.1	Imputation rules	14
5.1.1	Study drug	14
5.1.2	AE date imputation	14
5.1.3	Concomitant medication date imputation	16
5.2	AEs coding/grading	17
5.3	Laboratory parameters derivations	18
5.4	Statistical models	18
5.5	Rule of exclusion criteria of analysis sets.....	18
6	Reference.....	18

List of abbreviations

AE	Adverse event
TEAE	Treatment emergent adverse event
CRF	Case Report/Record Form
CPO	Country Pharma Organization
CRO	Contract Research Organization
CSR	Clinical Study Report
DS&E	Drug Safety and Epidemiology
ICH	International Conference on Harmonization
IEC	Independent Ethics Committee
MedDRA	Medical Dictionary for Drug Regulatory Affairs
MTX	Methotrexate
NSAID	Non-steroidal anti-inflammatory drug
RAP	Report and Analysis Process
SAE	Serious adverse event
SAP	Statistical Analysis Plan

Introduction

This document contains details of the statistical methods which will be used in the phase IV clinical trial CACZ885GFR01. This is an extension study to collect additional safety data (serious and non-serious adverse events) and to provide continuous Ilaris® (canakinumab) to patients in France who completed study CACZ885G2301E1, CACZ885N2301 or CACZ885G2306 until canakinumab (Ilaris®) is commercially available and reimbursed in France for these indications.

Data will be analyzed by Novartis and/or by the designated CRO and *statistical software SAS* version 9.4 according to the data analysis section 9 of the study protocol version 04 which is available in Appendix 16.1.1 of the CSR. Important information is given in the following sections and details are provided, as applicable, in Appendix 16.1.9 of the CSR.

Unless otherwise specified, the statistical methodologies including the analysis sets, analysis models, algorithms and conventions are following then interventional study protocol ACZ885GFR01.

The planned analysis is described in Section 9 of the protocol (Appendix 16.1.1 of CSR).

1.1 Study design

This is an open-label (single treatment arm) extension period for patients in France who have completed the international studies CACZ885G2301E1, CACZ885N2301 or CACZ885G2306. The last visit of CACZ885G2301E1, CACZ885N2301 or CACZ885G2306 studies will be the first visit of this extension study.

Patients follow up previously included in studies:

1. CACZ885G2301E1 (SJIA): These patients will continue the same dosing regimen as at the end of CACZ885G2301E1.
2. CACZ885N2301 (HPF indications: TRAPS, HIDS or crFMF): These patients will continue the maintenance dose as determined at the open-label period/ epoch 4 (i.e the lowest clinically efficacious does to maintain clinical efficacy in individual patients with a good tolerability).
3. CACZ885G2306 (SJIA indication): These patients will continue on their dosing regimen considered to constitute the lowest clinically efficacious does to maintain clinical efficacy in individual patients.

Visits will take place at scheduled administration dates, approximately every 4, 8 or 12 weeks. The safety of canakinumab (Ilaris®) will be evaluated (adverse events and serious adverse events collection). Patients will followed up according to SmPC with possible

adaptation based on investigators judgment related to specific patient medical consideration.

The study duration will depend on the date of reimbursement of canakinumab (Ilaris®) in France for the new indications and will be extended until the medication is commercially available for each indication. However, as the commercialization of the different indications may be effective at different dates, the patients will discontinue indication by indication (see section 5; end of treatment).

1.2 Study objectives and endpoints

The objective of this protocol is to collect additional safety data (serious and non-serious adverse events) and to provide continuous Ilaris® (canakinumab) treatment to patients in France who completed CACZ885G2301E1, CACZ885N2301 or CACZ885G2306 study.

The end of study is defined as premature termination or end of the study according to protocol: in the month following the availability of repaid product in France.

Visits will take place at scheduled administration date every 4, 6, 8 or 12 weeks (section 5). If no visit is performed within 12 weeks of previous injection, a control visit will be performed at week 13 +/- 7 days after the last administration in order to evaluate safety and need for the patient to continue the treatment and study.

Patients may voluntarily withdraw from study for any reason at any time. If premature withdrawal occurs, the investigator must make every effort to complete End of study visit in the CRF and to determine the primary reason for patient's premature withdrawal from the study and record this information.

2 Statistical methods

2.1 Data analysis general information

All categorical data will be presented in terms of frequencies and percentages. Summaries of continuous data will be presented in terms of mean, median, lower and upper quartile (for most variables), minimum and maximum, and the number of missing data points (for most variables) and the number of non- missing data points.

For descriptive statistics, the following number of decimal places will used: arithmetic mean, and median to 1 more decimal places than the raw data; minimum and maximum to the same number of decimal places as the raw data and SD to 2 more decimal places than the raw data. Percentages will be presented to 1 decimal place. Patient disposition, background and demographic characteristics.

2.1.1 General definitions

Study treatment: refers to: Ilaris = ACZ885

Study treatment start and end date: Study treatment start date is defined as the first date of study drug is administered and recorded on the Study Medication Dosing Record in CRF page. Similarly, study drug end date is defined as the last date of study drug is administered.

Study day: Study day will be calculated as (event date – study drug start date + 1 day) for events that occurred on or after study drug start date (e.g. visit, adverse events). For events prior to study drug start date (e.g., time of diagnosis), study day will be negative and calculated as (event date – study drug start date).

Baseline and post baseline: In general, a *baseline* value refers to the last measurement made prior to administration of the first dose of study treatment or the average values taken prior to administration of the first dose of study treatment. A post-baseline value refers to a measurement taken after the first dose of study treatment.

2.2 Analysis sets

Safety Set: Consists of all patients who received at least one dose of study drug and had at least one post-treatment safety assessment in the study. The statement that a patient had no adverse event (AE) also constitutes a safety assessment.

Analysis set	Population codes that cause subjects to be excluded	Non-PD criteria that cause subjects to be excluded
Safety	1	Did not provide informed consent, No treatment taken

Population code: 0=Include in everything, 1=Exclude from safety set

2.2.1 Subgroup of interest

All planned table will be repeated on following subgroup.

- Pathology: SJIA, HIDS/ MKD and FMF

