------------------	--

Investigational treatment	Novartis has been supplying the open-label investigational drug (canakinumab) under the form of a lyophilisate in vial. A marketing authorization has been granted in February 2017 by the European Commission for canakinumab as a solution for injection. If necessary (for logistic reasons), Novartis may supply one or the other pharmaceutical form for the trial. There will not be any change for the patient in the way the medication is administered (subcutaneously).
Efficacy assessments	There is no efficacy assessment in this study
Safety assessments	AEs and SAEs will be collected
Other assessments	None
Data analysis	
The data will be presented in a descriptive manner. Adverse events will be coded using the MedDRA dictionary that provides the primary system organ class and preferred term information.
 
Adverse events will be summarized for each indication by presenting the number and percentage of patients having any adverse event, having any adverse event in each primary system organ class and having each individual adverse event based on the preferred term. All other information collected (e.g. severity, relationship to study drug, or microorganism for infectious adverse events) will be tabulated and listed as appropriate.
 
Deaths, serious adverse events, and adverse events leading to discontinuation of study drug will be summarized by primary system organ class and preferred term and listed.
 
The exposure to study drug (number of injections) and duration of exposure (days) will be summarized and listed.

1 Introduction

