4.1 Inclusion criteria

Patients eligible for inclusion in this protocol have to fulfill all of the following criteria:

Criteria applicable for patients with Systemic Juvenil Idiopathic Arthritis (SJIA)

1. Patients who have completed the international CACZ885G2301E1 or CACZ885G2306 studies without any significant safety issue according to Investigator's opinion.
2. Patients who have completed the international CACZ885G2306 study and who successfully withdrew canakinumab treatment per protocol but with a disease relapse after the end of study visit will be allowed to participate in CACZ885GFR01 study (whatever the time of relapse from the end of study visit), if the investigator states that there is an indication to resume canakinumab.
3. Patients who have participated in the international CACZ885G2306 study but could not be randomized and then have continued canakinumab in part I until the end of the study at a dose of 4 mg/kg every 4 weeks may be switched to CACZ885GFR01 study if the investigator thinks that, in the interest of the patient, there is an indication to taper off canakinumab dose after a prolonged remission

Criteria applicable for patients with Periodic Fever syndromes (TRAPS, HIDS, crFMF)

1. Patients who have completed the international CACZ885N2301 study without any significant safety issue according to Investigator's opinion.

Criteria applicable for all patients

1. Parent's or legal guardian's written informed consent and child's assent, if appropriate, or patient's written informed consent for patients ≥ 18 years of age must be obtained before any study related activity or assessment is performed.

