2.14 Interim analysis

Not applicable

3 Sample size calculation

No sample size calculation was performed for this extension study which will include all eligible subjects who complete CACZ885G2301E1 or CACZ885N2301 study and meet the eligibility criteria.

4 Change to protocol specified analyses

Not applicable

5 Appendix

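### SAP 2.2.1 has no TRAPS level, so any TRAPS patient would be missing from the by-disease adverse event summary that the protocol requires; the SAP dose-count and age categories are also not open-ended

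*SAP*

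**What the plan says.** **Disease.** Protocol 9.4.1 states: "Adverse events will be summarized for each disease by presenting the number and percentage of patients having any adverse event". The synopsis has the same commitment in the form "Adverse events will be summarized for each indication by presenting the number and percentage of patients having any adverse event". Protocol 4.1 makes patients with TRAPS, HIDS or crFMF eligible if they completed CACZ885N2301, and SAP 1.1 names the same three indications. SAP 2.2.1 then says "All planned table will be repeated on following subgroup" and gives one line: "Pathology: SJIA, HIDS/ MKD and FMF". SAP section 4, headed "Change to protocol specified analyses", is answered as not applicable.

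**Dose counts.** SAP 2.4.1 classifies the number of doses, with injections in brackets as a synonym, into six bands from 1-4 to 21-24. Protocol 3.1 ties study duration to commercial availability for each indication and sets no fixed end.

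**Age.** SAP 2.3.3 uses four groups, the last running from 12 to below 20 years. Neither Protocol 4.1 nor 4.2 sets an upper age limit, and the consent criterion provides for patients aged 18 or over.

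**The concern.** Safety is the only data objective of this study, and reporting adverse events by disease is an explicit protocol commitment. A closed subgroup list that leaves out an eligible disease breaks that commitment without saying so. From the SAP alone, a reader cannot tell whether TRAPS was dropped because nobody with TRAPS enrolled or because it was overlooked.

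The dose and age lists raise a smaller problem of the same kind. A patient with more than 24 doses, or aged 20 or over, belongs to no category. The categorical rows would then not add up to the number in the safety set, and the programmer would have to improvise.

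**Working it through.** There is no sample size, power or test to reproduce. The check compares each category list with the population and duration that the documents allow.

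**1. Disease levels.** Eligible diseases (Protocol 4.1; SAP 1.1): SJIA, TRAPS, HIDS, crFMF, which is four. Levels in SAP 2.2.1, reading HIDS/MKD as HIDS and FMF as crFMF: three. The one left out is TRAPS. No pooled periodic-fever level and no residual level would catch it.

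**2. How many patients.** Protocol section 4 allows up to 8 patients from CACZ885N2301; the synopsis allows up to 7. The documents do not split these by disease, so the TRAPS number is between 0 and 8, or 0 and 7. Protocol 1.1 gives 46 TRAPS patients among 181 randomised in the parent study:

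- 46/181 = 25.4%
- 8 × 46/181 = 2.0; 7 × 46/181 = 1.8

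This is an illustration only. Nothing says that the French patients mirrored the worldwide mix.

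**3. Dose-count bands.** With dose 1 at week 0, dose 25 falls at week 24 × interval:

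| Interval | Week of dose 25 |
|---|---|
| 4 weeks | 96 |
| 6 weeks | 144 |
| 8 weeks | 192 |
| 12 weeks | 288 |

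Protocol 1.1 says that CACZ885G2301E1 was ending in November 2014, and its last visit is the first visit here. Assume a start between 1 and 30 November 2014. Adding 96 weeks (672 days) gives 3 September to 2 October 2016. Protocol 1.1 also reports an event of March 2017 as past while the study was still open. From 1 or 30 November 2014 to 1 or 31 March 2017 is 822 to 881 days. Whole 28-day intervals plus one give 30 to 32 administrations on uninterrupted 4-weekly dosing, above the last band. The SAP rows for other dose and no dose are regimen rows and do not hold counts above 24.

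**4. Age groups.** Protocol 1.1 gives the CACZ885G2306 entry range as 2 to below 20 years and an estimated maximum of 216 weeks for each study part.

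- 216 × 7 / 365.25 = 4.14 years
- 20 − 4.14 = 15.86 years

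A patient who entered at about 15.9 years or older and stayed 216 weeks would be 20 or over at the end. Under Protocol 4.1, patients who relapse after withdrawing canakinumab may enter at any later time, which allows higher ages. For CACZ885N2301 the protocol gives only a youngest age. This step assumes that age is taken at entry to the extension, as SAP 2.3.3 suggests by re-collecting date of birth and summarising data from this study's CRF.

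**The case against.** **The SAP defers to the protocol.** The SAP Introduction opens its general rule with "Unless otherwise specified, the statistical methodologies including the analysis sets" and follows the protocol from there. This does not repair the gap, because a named list of levels in 2.2.1 is itself a specification.

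**The sponsor may have known that no TRAPS patient enrolled.** This is plausible, and would make the list complete in practice. But neither document says so, and section 4 records no departure. What stands is that the consequence is conditional: the textual mismatch is certain, a real loss is not.

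**Size of the TRAPS group.** A reader might infer that up to 8/41 = 19.5% of the planned maximum (7/40 = 17.5% on the synopsis figures) is at risk. That would need every French CACZ885N2301 patient to have TRAPS, and the SAP itself plans tables for HIDS and FMF. The documents do not support using that ceiling as the expected size.

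**Counting injections.** A reader might also infer that the bands overflow at week 48, because Protocol 5.1.1 gives a 300 mg dose as two injections and Protocol 9.3 speaks of the number of injections. This is the less plausible reading. Protocol 6.2 collects the date of injection and the total volume, not separate injections, and SAP 2.4.1 counts doses by mg/kg level and lists dose dates. It would also apply only to uninterrupted 300 mg dosing every 4 weeks, and lower doses, longer intervals and interruptions are allowed. What remains is that the label should state its unit.

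**Dose and age categories breach no protocol rule.** This is correct. Protocol 9.2 and 9.3 prescribe no bands, so these two items are secondary table corrections.

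**Conclusion.** The TRAPS omission holds as a conflict between SAP 2.2.1 and Protocol 9.4.1. It affects 0 to 8 patients (0 to 7 by the synopsis), about 2 if the parent-study share applied. At zero, all that is missing is a sentence saying so.

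The dose-count bands and age groups are not exhaustive for what the documents allow. The dose result rests on an assumed November 2014 start and uninterrupted 4-weekly dosing; how many of the twelve CACZ885G2301E1 patients fit that is not stated. The age result shows that ages of 20 or over are possible. The documents do not say that any enrolled patient was that old.

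A reader might infer that such patients drop out of the safety evaluation. They do not: they stay in the overall safety-set tables, the listings, and the continuous summaries of age and exposure. Only the by-pathology and categorical tables are affected. The study is descriptive, so no error rate or test changes. The change should be made because a protocol commitment is involved and the correction is cheap, but the impact is low.

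**What to change.** - **SAP 2.2.1:** add TRAPS as a level. Alternatively, state that no TRAPS patient enrolled and record this in section 4.
- **SAP 2.4.1:** add a band of 25 or more, and state that the count is of administrations, consistent with the data collected under Protocol 6.2.
- **SAP 2.3.3:** add an age group of 20 years and over.

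The cost is wording and table-shell edits, with no new data and no change of method. The downside is that some rows may be empty or hold very few patients.
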